Intra-patient dose escalation will be adopted in Cohort 5; the CRC will evaluate the safety, clinical observations and PK data following cycle 1 (dosed at 8mg/kg) and approve escalation to 16 mg/kg on Cycle 4 Day 1. Based on the review of the safety data, the CRC may suggest an alternative dose regimen for the patient if required, to a maximum of 16 mg/kg. If a DLT occurs at 8 mg/kg requiring dose de-escalation, subsequent doses may be reduced. If a DLT occurs at 16 mg/kg, subsequent doses may also be reduced.

Cohort 6 will enroll a further 3 patients at a dose of up to 16 mg/kg; the dose will be decided upon by the CRC guided by safety, PK and PD data available from Cohort 5.

Once the MTD/MAD has been established for a given dose and schedule, up to 12 additional patients with incurable, locally advanced prostate cancer or other advanced solid tumors may be enrolled at this dose level (termed as “Enrichment Cohort”).

Thirty evaluable patients will be enrolled for the dose escalation part of the study and no more than 12 patients for the enrichment part of the study at the defined MTD/MAD for a total of 42 patients.

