4.2.1 Intent to Treat set

All subjects that received at least one dose of VAL201 will be included. Patients enrolled for the dose escalation part of the study will be replaced if they withdraw for reasons other than a DLT associated event.

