4.2.3 Safety set

The safety set will include all patients that have been given at least one dose by subcutaneous (s.c.) injection of VAL201.

Forms				
Title		Statistical Analysis Plan Template		
Code		Version	Effective Date	Page
FRM_ST03_032		01	23 Apr 2015	14 of 24

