4.4 Handling of missing and incomplete data

Missing values will be included in the denominator count when computing percentages. Only the non-missing values will be evaluated for computing summary statistics. AEs that have missing onset dates will be considered to be treatment-emergent, unless the stop date is known to be prior to the first administration of VAL201.

In order to calculate the duration of tumor, the following rules will be applied for partial dates of histological/cytological diagnosis:

- if only the day is missing, the 15th of the month will be assumed;
- if the day and the month are missing, 30th June will be assumed.

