5.3 Study discontinuations

As it is stated on section 3.4 of study protocol: if a patient is withdrawn from the study for reasons other than a DLT-associated event before the end of cycle 1 during the dose escalation portion of the study, the patient will be replaced; whereas patients who withdraw from the study or discontinue treatment after completion of cycle 1 will not be replaced.

The number of subject withdrawals and the number of subjects completing the study will be summarized. This summary will include the reasons for discontinuation.

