5.12 Tumour assessment prostate

Tumour assessment for prostate cancer patients will follow the PCWG2 guidelines or RECIST 1.1 guidelines and may include assessment of serum prostate-specific antigen (PSA) at screening and every 3 weeks or at the end of every cycle.

Forms				
Title		Statistical Analysis Plan Template		
Code		Version	Effective Date	Page
FRM_ST03_032		01	23 Apr 2015	19 of 24

A summary table for tumour assessment at screening and at each applicable cycle will be produced presenting descriptive statistics for longest tumour diameter (mm) reported as well as duration of tumour (years) and method of examination; longest tumour diameter will be classified by tumour location and such categories will be defined by a study medical expert reviewing the related information collected.

The assessment of prostate-specific antigen PSA outcomes will be summarised for each patient and time point including the percent change in PSA from baseline to tumour assessment time point.

An estimate of pre-treatment PSA doubling time will be presented in a summary table together with descriptive statistics for PSA values at each cycle and the related percent change from baseline.

Baseline PSA value is defined as the last available assessment before treatment start (which will be actually the PSA value collected at Cycle 1 Day 1).

Thereafter tumour assessment and prostate-specific antigen PSA assessment results will be listed, including also maximum decline in PSA during study.

If other methods were used to assess the tumour such CT scan or MRI then the results of the tests will be listed for each patient by time point.

6. Evaluation of objectives

The evaluation of the primary objective will be based on the safety set, the evaluation of the secondary objective will be based on the ITT set and the evaluation of the exploratory objective will be based on the ITT set and the PP set separately. Tables and listings will be presented separately.

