6.1 Analysis of primary objective

The primary objective of this study is to estimate the MTD/MAD of VAL201 throughout an accelerated dose escalation design (3+3 patients per dose level). The first 2 cohorts will enroll 1 patient only (see Section 1.5 of the study protocol). For each cohort, patients will be followed up for adverse events (AEs) and DLT during each cycle.

The escalating dose will be determined if 0 patients out of 3 or 1 patient out of 6 experience a DLT, and de-escalating if 2 or more patients with DLTs are encountered. Therefore the MTD will be the highest dose level at which 0 of 3 or 1 of 6 patients experience a DLT.

The CRC will review all patient safety data at the end of Cycle 1 and only permit dose escalation to the next dose level where there are no safety concerns. Where the CRC suspects that drug-related events have occurred that merit further exploration at that dose level, they will request that Cohort 1 or 2 must enroll 3 more patients in order to more thoroughly evaluate safety events prior to escalation. Cohorts of 3 patients will be enrolled from the 3rd cohort onwards (or earlier where the CRC recommend due to safety data evaluation) thereafter the cohort will be expanded to 6 patients upon identification of a DLT. If a second DLT is reported this will be declared the MTD.

There will be no formal statistical analysis in the dose-escalation phase. However, safety data such as AEs and DLT will be listed and summarised by dose level separately using descriptive statistics. Pre-treatment AEs will be listed.

Forms				
Title		Statistical Analysis Plan Template		
Code		Version	Effective Date	Page
FRM_ST03_032		01	23 Apr 2015	20 of 24

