7.2 Tables listings and figures

7.2.1 Tables:

 cros nt	Forms			
	Title	Statistical Analysis Plan Template		
	Code	Version	Effective Date	Page
	FRM_ST03_032	01	23 Apr 2015	22 of 24

TABLE 14.1-1	DISPOSITION OF PATIENTS / SUMMARY OF ALL PATIENTS AND ANALYSIS SET
TABLE 14.1-2.1	SUMMARY OF MAJOR PROTOCOL DEVIATION / INTENT TO TREAT POPULATION
TABLE 14.1-2.2	SUMMARY OF MINOR PROTOCOL DEVIATION / INTENT TO TREAT POPULATION
TABLE 14.1-3.1	DEMOGRAPHIC CHARACTERISTIC / INTENT TO TREAT POPULATION
TABLE 14.1-4	SUMMARY OF TUMOUR ASSESSMENT / INTENT TO TREAT POPULATION
TABLE 14.1-5.1	MEDICAL HISTORY BY SYSTEM ORGAN CLASS AND PREFERRED TERM / INTENT TO TREAT POPULATION
TABLE 14.1-5.2	CONCOMITANT DISEASE BY SYSTEM ORGAN CLASS AND PREFERRED TERM / INTENT TO TREAT POPULATION
TABLE 14.1-6.1	PREVIOUS MEDICATIONS / INTENT TO TREAT POPULATION
TABLE 14.1-6.2	CONCOMITANT MEDICATIONS / INTENT TO TREAT POPULATION
TABLE 14.2-1	SUMMARY OF DOSE LIMITING TOXICITY (DLT) BY COHORT / SAFETY POPULATION
TABLE 14.2-3.1	PROSTATE SPECIFIC ANTIGEN (PSA) ASSESSMENT / INTENT TO TREAT POPULATION
TABLE 14.2-3.2	PROSTATE SPECIFIC ANTIGEN (PSA) ASSESSMENT / PER PROTOCOL POPULATION
TABLE T14.2-4.1	SUMMARY OF RESPONSE RATE ANTI TUMOUR ACTIVITY / INENT TO TREAT POPULATION
TABLE T14.2-4.2	SUMMARY OF RESPONSE RATE ANTI TUMOUR ACTIVITY / PER PROTOCOL POPULATION
TABLE T14.3.1-1.1	SUMMARY OF TREATMENT-EMERGENT ADVERSE EVENTS BY DOSE/ DOSE ESCALATION SAFETY POPULATION
TABLE T14.3.1-2.1	SUMMARY OF TREATMENT EMERGENT ADVERSE EVENT BY SYSTEM ORGAN CLASS AND BY DOSE / DOSE ESCALATION SAFETY POPULATION
TABLE T14.3.1-3.1	SUMMARY OF TREATMENT EMERGENT ADVERSE EVENT BY SYSTEM ORGAN CLASS AND BY SEVERITY / DOSE ESCALATION SAFETY POPULATION
TABLE T14.3.1-4.1	SUMMARY OF TREATMENT EMERGENT ADVERSE EVENT BY SYSTEM ORGAN CLASS AND BY CAUSALITY / DOSE ESCALATION SAFETY POPULATION
TABLE 14.3.4-1.1	ESTERN CO-OPERATIVE ONCOLOGY GROUP (ECOG) PERFORMANCE STATUS / INTENT TO TREAT POPULATION
TABLE 14.3.4-1.2	ESTERN CO-OPERATIVE ONCOLOGY GROUP (ECOG) PERFORMANCE STATUS / PER PROTOCOL POPULATION
TABLE 14.3.4-2.1	SUMMARY VITAL SIGNS BY CYCLE AND VISIT / INTENT TO TREAT POPULATION

 cros nt	Forms			
	Title	Statistical Analysis Plan Template		
	Code	Version	Effective Date	Page
	FRM_ST03_032	01	23 Apr 2015	23 of 24

TABLE 14.3.4-2.2	SUMMARY VITAL SIGNS BY CYCLE AND VISIT / PER PROTOCOL POPULATION
TABLE 14.3.4-3.1.1	LABORATORY PARAMETERS: CLINICAL CHEMISTRY BY CYCLE AND TIME POINTS / INTENT TO TREAT POPULATION

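### The primary DLT and MTD/MAD evaluation uses the safety set, so a dosed patient who was replaced stays in the DLT denominator beside the replacement and any non-zero DLT proportion is understated

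*SAP*

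**What the plan says.** - **Set for the primary objective (Section 6).** "The evaluation of the primary objective will be based on the safety set".
- **Definition of that set (4.2.3).** "The safety set will include all patients that have been given at least one dose by subcutaneous (s.c.) injection of VAL201". No minimum exposure or DLT follow-up is required.
- **Output (7.2.1).** Table 14.2-1 is titled "SUMMARY OF DOSE LIMITING TOXICITY (DLT) BY COHORT / SAFETY POPULATION".
- **MTD rule (6.1, also 3.3).** "the MTD will be the highest dose level at which 0 of 3 or 1 of 6 patients experience a DLT".
- **Replacement, with a time limit (5.3, citing protocol section 3.4).** A replacement is made "if a patient is withdrawn from the study for reasons other than a DLT-associated event before the end of cycle 1"; patients who leave later are not replaced.
- **Replacement, without a time limit (4.2.1).** Dose-escalation patients "will be replaced if they withdraw for reasons other than a DLT associated event".
- **Planned number (3.1).** "Thirty evaluable patients will be enrolled for the dose escalation part of the study". The SAP does not define evaluable in this sense. The sets in 4.2 are ITT, per protocol, safety and PK.
- **Denominators (4.4).** "Missing values will be included in the denominator count when computing percentages".

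**The concern.** A 3+3 rule is a statement about patients who were observed long enough to show a DLT. Replacing early non-DLT withdrawals, and planning a number of evaluable patients, only makes sense if the replaced patient does not fill one of the 3 or 6 places. The analysis set does not follow that logic. It keeps everyone with one dose, and nothing in the SAP removes a replaced patient from the DLT denominator. That patient contributes no DLT and one unit of denominator, although follow-up for DLT was incomplete.

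The DLT table is the main statistical output for the primary objective. If its denominators are not the ones the rule refers to, a reader of the study report cannot trace the declared MTD or MAD from the table to the rule. Any non-zero DLT proportion in it can only err downwards.

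**Working it through.** **1. The plan's own figures presuppose exactly 3 or 6 counted patients.** Section 3.3 tabulates the probability of escalation. With escalation on 0/3, or on 1/3 followed by 0/3, and true DLT rate p:

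P(escalate) = (1−p)³ + 3p(1−p)² × (1−p)³

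| p | Calculation | Result | SAP 3.3 |
|---|---|---|---|
| 20% | 0.512 + 0.384 × 0.512 | 70.9% | 71% |
| 30% | 0.343 + 0.441 × 0.343 | 49.4% | 49% |
| 40% | 0.216 + 0.432 × 0.216 | 30.9% | 31% |
| 50% | 0.125 + 0.375 × 0.125 | 17.2% | 17% |
| 60% | 0.064 + 0.288 × 0.064 | 8.2% | 8% |

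All five values reproduce. The formula has no place for a fourth or seventh patient who was dosed but not fully observed.

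**2. What the safety set does to the denominator.** Let x be the patients with a DLT, n the 3 or 6 patients the rule counts, and m the patients dosed and then replaced at that level. The rule refers to x/n; Table 14.2-1 on the safety set gives x/(n+m).

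| Rule (x/n) | m = 1 | m = 2 | m = 3 |
|---|---|---|---|
| 0/3 = 0% | 0/4 = 0% | 0/5 = 0% | 0/6 = 0% |
| 1/6 = 16.7% | 1/7 = 14.3% | 1/8 = 12.5% | 1/9 = 11.1% |
| 2/6 = 33.3% | 2/7 = 28.6% | 2/8 = 25.0% | 2/9 = 22.2% |

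A non-zero proportion falls by the fraction m/(n+m): one seventh for one replaced patient in a level of six, one quarter for two. A zero stays zero, but its denominator no longer matches the rule.

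**3. What does not change.** The replaced patient left for a non-DLT reason and is additional to the 3 or 6, so x is the same in both columns. Two DLTs remain two DLTs whether printed as 2/6 or 2/8.

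**4. How often it could arise.** The SAP gives no early-withdrawal rate. Assuming 5%, 10% or 20% per patient, independently, the chance of at least one such patient among the first six at a level is 1 − (1−d)⁶ = 27%, 47% or 74%. These rates are assumptions, not trial data.

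**5. The boundary of the set is not fixed either.** Sections 4.2.1 and 5.3 differ on whether a non-DLT withdrawal after Cycle 1 is replaced. Section 3.5 ties two DLT criteria to Cycle 1 (failure to deliver the Cycle 1 doses as planned, and a related delay of more than 7 days in that cycle), and 6.1 places the committee's review at the end of Cycle 1. Sections 3.1, 4.6 and 6.1 have DLTs followed in every cycle. From this text a programmer cannot derive who was fully observed for DLT.

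**The case against.** The strongest counter-argument is that the MTD conclusion is unaffected. The triggers are counts: a first DLT expands the cohort, and two or more patients with DLTs lead to de-escalation. Retained patients add none. Escalation was decided during the trial by the Cohort Review Committee on all available safety data, and this SAP version (July 2020) postdates the closure of recruitment (January 2020). This stands, and it limits the point to reporting.

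Other parts also stand:

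- That replaced patients are not evaluable is an inference from the replacement rule and the planned number of evaluable patients. The SAP does not say it outright.
- Denominators of 1 or 4 occur by design in Cohorts 1 and 2, which enrol one patient and may add three. An unusual denominator is therefore not in itself a sign of a retained replacement.
- Disposition and withdrawal reasons are summarised and listed, so a careful reader could identify early withdrawals.
- The protocol may define DLT evaluability. The point here rests on the set the SAP does name for the primary objective and the DLT table.

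Three stronger readings are tempting but unsupported. A reader might infer that the rule can no longer be applied; it can, because the counts survive. A reader might infer that escalation became more likely at toxic doses; that would require early withdrawals to occupy the 3 or 6 places, whereas the plan replaces them. A reader might infer that a DLT confidence limit becomes falsely tight; the exact 95% interval is planned for the response rate only, and 6.1 keeps the DLT analysis descriptive.

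**Conclusion.** The point holds as a moderate defect in a stated analysis set. On the text, the primary DLT summary counts every dosed patient, including those the design replaces. With one replaced patient in a level of six, the reported proportion drops from 16.7% to 14.3% (one DLT) or from 33.3% to 28.6% (two DLTs), and the table departs from the 0/3 and 1/6 rule. The error can only run downwards.

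This rests on two assumptions: that replaced patients are not meant to count toward the 3 or 6, and that at least one dosed patient was replaced at a level. The documents do not report the second, and without it the numerical effect is nil. The conflicts over replacement and the observation period exist either way. The documents do not support a claim that the MTD itself, or any dose decision, was biased.

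**What to change.** - Add a DLT-evaluable set to 4.2: dosed patients who had a DLT or who completed the DLT observation period stated in the protocol.
- Name this set in Section 6 for the primary objective, and use it for Table 14.2-1 and the MTD/MAD statement.
- Keep the safety set for the AE tables, and flag or list replaced patients with their cohort and reason for withdrawal.
- Reconcile the replacement sentence in 4.2.1 with 5.3.
- Reconcile the Cycle 1 DLT criteria and committee review (3.5, 6.1) with DLT follow-up in each cycle (3.1, 4.6, 6.1), so that the observation period is unambiguous. The new set should not simply be defined by completing Cycle 1: DLTs are followed beyond it, and failure to deliver the planned Cycle 1 doses is itself a DLT consideration, so some non-completers may already count as DLTs. Which period applies is for the sponsor to settle against the protocol.

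The cost is a few lines of SAP text, one population flag and one changed table header. No new data are needed.

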6.1 Analysis of primary objective

The primary objective of this study is to estimate the MTD/MAD of VAL201 throughout an accelerated dose escalation design (3+3 patients per dose level). The first 2 cohorts will enroll 1 patient only (see Section 1.5 of the study protocol). For each cohort, patients will be followed up for adverse events (AEs) and DLT during each cycle.

The escalating dose will be determined if 0 patients out of 3 or 1 patient out of 6 experience a DLT, and de-escalating if 2 or more patients with DLTs are encountered. Therefore the MTD will be the highest dose level at which 0 of 3 or 1 of 6 patients experience a DLT.

The CRC will review all patient safety data at the end of Cycle 1 and only permit dose escalation to the next dose level where there are no safety concerns. Where the CRC suspects that drug-related events have occurred that merit further exploration at that dose level, they will request that Cohort 1 or 2 must enroll 3 more patients in order to more thoroughly evaluate safety events prior to escalation. Cohorts of 3 patients will be enrolled from the 3rd cohort onwards (or earlier where the CRC recommend due to safety data evaluation) thereafter the cohort will be expanded to 6 patients upon identification of a DLT. If a second DLT is reported this will be declared the MTD.

There will be no formal statistical analysis in the dose-escalation phase. However, safety data such as AEs and DLT will be listed and summarised by dose level separately using descriptive statistics. Pre-treatment AEs will be listed.

Forms				
Title		Statistical Analysis Plan Template		
Code		Version	Effective Date	Page
FRM_ST03_032		01	23 Apr 2015	20 of 24

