2.1.1 Primary objective

The primary objective of this clinical study is to estimate the Maximum Tolerated Dose (MTD)/Maximum Administered Dose (MAD) of VAL201 in cancer patients with advanced solid tumors.

MTD refers to a dose with an acceptable and manageable safety profile, in the absence of the MTD
MAD refers to the highest dose level administered.

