3.3 Sample size justification

Up to 42 patients with incurable, locally advanced or metastatic prostate cancer or other advanced solid tumours may be enrolled in this study. It will follow a dose escalation design, and the number of patients treated will therefore be dependent upon the number of dose levels investigated. A conventional algorithm (3+3 patients per dose level) will be used to identify the MTD or MAD, escalating on 0/3 or 1/6 DLTs, and de-escalating if 2 or more patients with DLTs are encountered. The MTD will be the highest dose level at which 0 of 3 or 1 of 6 patients experience a DLT, with the next higher dose having at least 2 of 3 or 2 of 6 patients experiencing a DLT.

The following table shows the operating characteristics of this 3+3 design. Under this design, there is a 71% chance of escalation if the true but unknown rate of DLT is 20% and less than 50% chance of escalation if the true but unknown rate of DLT is higher than 30%.

Operating characteristics of the 3+3 study design

True but Unknown Rate of DLT (%)	Probability of Escalation (%)
20	71
30	49
40	31
50	17
60	8

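### SAP 3.1 and 6.1 name the dose with a second DLT as the MTD, against the 0 of 3 or 1 of 6 rule in 3.3 and in 6.1 itself

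*SAP*

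**What the plan says.** Sections 3.1 and 6.1 of the SAP both describe a cohort of three that is expanded to six once a DLT is identified, and both continue: "If a second DLT is reported this will be declared the MTD".

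The preceding paragraph of 6.1 gives a different rule: "and de-escalating if 2 or more patients with DLTs are encountered", followed by "Therefore the MTD will be the highest dose level at which 0 of 3 or 1 of 6 patients experience a DLT".

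Section 3.3 agrees with that rule ("escalating on 0/3 or 1/6 DLTs, and de-escalating if 2 or more patients with DLTs are encountered") and completes the definition by placing the failing dose one step above the MTD: "with the next higher dose having at least 2 of 3 or 2 of 6 patients experiencing a DLT".

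Section 2.1.1 describes the two terms in the objective: "MTD refers to a dose with an acceptable and manageable safety profile", and, where there is no MTD, "MAD refers to the highest dose level administered".

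Three further provisions bear on the counting. Section 3.1 plans for Cohort 5 to move within patient from 8 to 16 mg/kg at Cycle 4. Section 4.1 assigns each patient, cycle by cycle, to the dose taken most often in that cycle. Section 6.1 promises DLT summaries by dose level, but Table 14.2-1 in section 7.2.1 is by cohort.

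**The concern.** The only dose in view in the second-DLT sentence is that of the expanded cohort, so the word *this* refers to it. A dose with DLTs in two of six patients cannot be the MTD under one sentence and lie above the MTD under another, and nothing in the SAP says which governs.

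The MTD/MAD is the sole primary objective. If two patients had DLTs at one level, the report could name that level as tolerated by following one sentence of 6.1, or rule it out by following another.

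The sentence also counts DLTs within a cohort, whereas the definition counts patients within a dose level. In Cohort 5 one DLT at 8 mg/kg and one at 16 mg/kg would make two in the cohort but not two at either dose.

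**Working it through.** **1. The plan's own figures.** Inputs: the rule in 3.3 (escalate on 0 of 3, or on 1 of 3 followed by 0 of 3) and the true DLT rates p in its table. With q = 1 − p,

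P(escalate) = q³ + 3pq² × q³.

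For p = 0.2: 0.512 + 0.384 × 0.512 = 0.709. The other rates follow in the same way, and all five reproduce the table:

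| True DLT rate | 20% | 30% | 40% | 50% | 60% |
|---|---|---|---|---|---|
| SAP 3.3, P(escalate) | 71 | 49 | 31 | 17 | 8 |
| Recomputed | 70.9 | 49.4 | 30.9 | 17.2 | 8.2 |
| Complement: two or more patients with DLTs | 29.1 | 50.6 | 69.1 | 82.8 | 91.8 |
| 1 of 3, then at least one more in the next three | 18.7 | 29.0 | 33.9 | 32.8 | 27.0 |

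The last row is 3pq² × (1 − q³), the path that the sentence itself describes; for p = 0.2 it is 0.384 × 0.488 = 0.187. The table is correct and the fix leaves it unchanged. It shows when escalation stops, not which dose is then called the MTD.

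**2. The rules side by side.** Suppose two of six patients have DLTs at dose level k.

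- Second-DLT sentence (3.1, 6.1): level k is the MTD.
- De-escalation rule (3.3, 6.1): go down from level k.
- Definition (3.3, 6.1): the MTD has 0 of 3 or 1 of 6, so it is not level k.
- Next-higher-dose condition (3.3): level k is the level above the MTD.
- Meaning of the term (2.1.1): a dose with an acceptable safety profile, which fits the definition better than the sentence.

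The second-DLT sentence stands alone against the others.

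**3. What the difference amounts to.** A level with two of six has an observed DLT rate of 2/6 = 33% (exact 95% CI 4% to 78%). A six-patient level that meets the definition has at most 1/6 = 17% (0.4% to 64%). The intervals overlap widely, so six patients cannot show that two such doses differ; the point is which dose the rule names.

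**4. Example with the SAP's doses.** Assume that two patients have DLTs at 16 mg/kg.

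- The sentence reports 16 mg/kg as the MTD.
- Section 3.3 reports 8 mg/kg, if that is the next lower level and has 0 of 3 or 1 of 6. The two answers differ by a factor 16/8 = 2.
- If no lower level qualifies, 3.3 yields no MTD. The MAD of 2.1.1 then applies, and as the highest dose given it is again 16 mg/kg, under another label. Cohorts 1 and 2 may hold one patient each, so a lower level need not have three patients.

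**5. The definition in 6.1.** It leaves out the next-higher-dose condition of 3.3. A top dose with 0 of 3 or 1 of 6 and nothing tested above it is therefore an MTD by 6.1 but does not meet the definition in 3.3. The dose is the same; only its label changes.

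**The case against.** The strongest reply is that this is a slip of wording beside a clear rule. The 0 of 3 or 1 of 6 definition appears twice, both times with de-escalation at two or more patients, and the disputed sentence gives no counts. It may be a loose way of saying that the MTD has been passed. Section 3.1 also refers the escalation rules to protocol section 4.2, which was not available here. Much of this stands: the intended rule is hardly in doubt. But the sentence says something else, in both the design section and the primary analysis section, so it still needs correcting.

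It is also fair that a second DLT need not be a second patient. DLTs are followed in every cycle, and two in one patient would be 1 of 6. This stands, so the sentence names a dose at which two of six *may* have had DLTs, not one at which they must have.

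On Cohort 5, sections 4.1 and 6.1 already separate patients by actual dose. What remains is the by-cohort layout of Table 14.2-1 and the cohort-based wording of the sentence.

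Finally, little now depends on the sentence. Recruitment closed in January 2020 (section 1), the enrichment phase was not reached (4.6), and the SAP does not say that any DLT occurred. This stands and limits the weight of the point.

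**Conclusion.** The second-DLT sentence in 3.1 and 6.1 contradicts 3.3 and the definition in 6.1, and is wrong as written for the sole primary objective. The effect is on the report's MTD conclusion only, and only if two patients had DLTs at one dose level. For a full 3+3 level the chance of that is 29% to 92% over true DLT rates of 20% to 60%. These figures assume independent patients, a common true rate and no one-patient cohort; they are not estimates for this trial.

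Four stronger readings are not supported:

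- A reader might infer that the escalation table proves which dose is the MTD. It does not: both readings stop escalation at two patients with DLTs and differ only in the dose they name.
- A reader might infer that the two rules always differ by one dose level. They do not: the next lower level may fail to qualify, and the MAD may then be the same dose that the sentence names.
- A reader might infer that 2.1.1 by itself makes a clean top dose a MAD. It does not: it brings in the MAD only when there is no MTD, and only 3.3 carries the next-higher-dose condition.
- A reader might infer that the trial reported a wrong MTD. Nothing in the SAP shows this.

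**What to change.** In 3.1 and 6.1 replace the second-DLT sentence with:

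*If 2 or more patients have a DLT at a dose level, that dose exceeds the MTD; the MTD is the highest lower level with a DLT in 0 of 3 or 1 of 6 patients. If no MTD can be established, the MAD (highest dose administered) is reported as defined in 2.1.1, with a statement of whether 2 or more patients had DLTs at that dose.*

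The closing statement matters because the MAD may itself be a dose with two DLT patients.

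Count patients with DLTs by dose level, using the per-cycle actual-dose assignment already in 4.1, so that Table 14.2-1 shows Cohort 5 separately at 8 and 16 mg/kg. A rule based on the dose at onset should not be added, since it can differ from the most frequent dose in the cycle. Add the next-higher-dose condition of 3.3 to the MTD definition in 6.1.

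The cost is SAP wording and a dose split in one table, with no new data or patients. If the SAP is not reopened, the same rule can be stated in the clinical study report, where section 1 already requires deviations to be explained.
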